### **3. SUMMARY OF STUDY PLAN**

This will be a Phase I, non-randomized, dose escalation study in patients with node positive non-metastatic HER2 negative breast cancer that are in remission and defined as no evidence of disease (NED). The study will accrue 30 evaluable patients with up to 12 patients in each dose arm.

Patients will be assigned sequentially to one of three arms defined by vaccine dose. Patients will be accrued to Arm 1 first, then Arm 2, then Arm 3. Each dose arm will have a staggered enrollment. There will be one week between the first patient's vaccination 1 visit and second patient's vaccination 1 visit to each dose arm to ensure no toxicities. Furthermore, three patients will initially be enrolled to a dose arm, receive the first vaccine, and be evaluated for toxicity prior to the second vaccine (1 month of monitoring) before the remaining patients will be enrolled in that dose arm.

If there is sufficient evidence (please refer to Section 8.5.1“Accrual and Criterion for Premature Study termination”.) to suggest the Arm 1 dose is safe (Section 13.1), then the Arm 2 cohort of up to 12 patients will be enrolled. If the Arm 2 dose is also sufficiently safe then enrollment into the Arm 3 dose may move forward. If the Arm 3 dose appears safe, the immunologic efficacy among three dose groups will be examined to determine the recommended phase 2 vaccine dose for further cancer prevention studies. Immunologic efficacy of the 3 WOKVAC doses, will be evaluated by an assessment of the generation of cellular and humoral response to IGFBP-2, HER2, and IGF-1R, development of persistent T cell memory; and modulation of Tregs and MDSC with vaccination as described in Section 13.5.

We will be evaluating the effect of the WOKVAC vaccine on the heart by measuring left ventricular ejection fraction (LVEF) with a MUGA or ECHO before vaccination, one month after the first vaccine, and one month after the vaccination series.

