Clinical and autoimmune labs will be drawn prior to each vaccine and 1 month and 6 months following the last vaccine to evaluate for safety. Patients are monitored for the development of toxicities by assessing adverse events (AE's) with serum chemistries, liver function studies, and complete blood counts. Adverse events for all systems are graded on a scale of 1-5 using the Common Terminology Criteria for Adverse Events Version 4.0 (CTCAE v4.0). We will be using the Cancer Therapy Evaluation Program (CTEP), National Cancer Institute (NCI) Guidelines for reporting adverse events assigning attribution (unrelated, unlikely, possible, probable, definite) Blood samples to test the effect on the immune system will be drawn at baseline, and 1 month (28±7 days) and 6 months (168±14 days) following the last vaccine. The specific measurements being done to evaluate immune response are memory T cell response, modulation of Treg, and MDSC.

The duration of the study will be 5 years, which includes annual follow-up from enrollment, with the subject's primary oncologist or primary care physician. Long-term follow up data, beyond the 6 month follow-up visit, will be kept and managed by the IND Sponsor at the University of Washington.

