#### 8.5.1. Criteria for Premature Study Termination

Benchmarks for the safety of a dose level will be that there are no attributable (definitely, probably and possibly-related to study drug) grade 4 toxicity and <30% incidence of attributable Grade 3 toxicity (definitely, probably and possibly related to the study agent except as noted in the table below). If the observed rate of each of these toxicities is consistent with these benchmarks, escalation to the next higher dose level will be allowed.

Escalation will not be allowed if the observed toxicity rate exceeds the above. Other participants at the same dose level without toxicities will be allowed to continue at that dose level.

For grade 1 or 2 vaccine-related reactions, patients may be treated with acetaminophen or diphenhydramine as clinically indicated at the discretion of the study clinician and continue to receive vaccinations. For this prevention study  $\geq$  grade 3 attributable toxicity (other than those listed below; CTEP CTCAE v4.0) is considered dose-limiting for the patient. If grade 3 toxicity that is at least possibly related to the vaccine (except as described below) is observed, no further immunizations will be administered to that patient.

If  $\geq 3$  participants experience a grade 3 attributable toxicity, except as noted in the table below, or if any participant experiences a grade 4 attributable toxicity within any dose level, further accrual at that dose level will stop and accrual to the study will be terminated.

Category	Grade 3 Attributable Toxicity/AE	Allowable Duration
General disorders and administration	Flu-like symptoms	1 week
Musculoskeletal and connective tissue disorders	Arthralgia	1 week
	Myalgia	1 week
Investigations	Lymphocyte count decreased	2 weeks
	Platelet count decreased	1 week
	Hemoglobin decrease	1 week
	White blood cells decreased	2 weeks

We would consider a grade 3 or 4 autoimmune event a dose limiting toxicity and would consider steroid administration for grade 3 or 4 adverse immune related events that have been reported with other immune based therapies, i.e. ipilimumab. Examples of such immune related AEs include; rash, diarrhea/colitis, and hepatitis. The following dose schedule may be used:

Day 1-2: Intravenous Solu-Medrol at 1 mg/kg  
Day 3-4: Prednisone at 30 mg BID PO q day  
Day 4-5: Prednisone at 15 mg BID PO q day  
Day 5-6: Prednisone at 10 mg BID PO q day  
Day 6-7: Prednisone at 10 mg PO q day  
Day 8-9: Prednisone at 5 mg PO q day

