## CTCAE v.4.0 general severity guidelines:

Grade	Severity	Description
1	Mild	Mild; asymptomatic or mild symptoms; clinical or diagnostic observations only; intervention not indicated.
2	Moderate	Moderate; minimal, local or noninvasive intervention indicated; limiting age-appropriate instrumental activities of daily living (ADL)*.
3	Severe	Severe or medically significant but not immediately life-threatening; hospitalization or prolongation of hospitalization indicated; disabling; limiting self-care ADL**.
4	Life-threatening	Life-threatening consequences; urgent intervention indicated.
5	Fatal	Death related to AE.

\*Instrumental activities of daily living (ADL) refers to preparing meals, shopping for groceries or clothes, using the telephone, managing money, *etc.*

\*\*Self-care ADL refers to bathing, dressing and undressing, feeding self, using the toilet, taking medications, and not bedridden.

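### Section 8.5.1 names grade 4 but not grade 5 in its escalation and accrual-stop rules, so read literally an attributable death recorded only as grade 5 triggers neither

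*Combined protocol and SAP*

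**What the plan says.** Section 8.5.1 of the combined protocol and SAP sets two rules at dose level.

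- **Escalation.** The benchmark is no attributable "grade 4 toxicity and <30% incidence of attributable Grade 3 toxicity". The section continues: "If the observed rate of each of these toxicities is consistent with these benchmarks, escalation to the next higher dose level will be allowed". It then adds: "Escalation will not be allowed if the observed toxicity rate exceeds the above".
- **Accrual.** Accrual stops, and the study is terminated, when at least three participants have attributable grade 3 toxicity outside the table of exceptions, or "if any participant experiences a grade 4 attributable toxicity within any dose level, further accrual at that dose level will stop".

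The same section has a patient-level rule. Attributable toxicity of grade 3 or above is dose-limiting for that patient, and the next sentence reads: "If grade 3 toxicity that is at least possibly related to the vaccine (except as described below) is observed, no further immunizations" will be given to that patient.

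On grading, Section 3 states: "Adverse events for all systems are graded on a scale of 1-5". The severity table under Section 11.1.3 lists grade 4 as life-threatening and, separately, grade 5 as fatal, described as "Death related to AE".

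Sections 3, 13.1 and 13.10 send the escalation decision back to Section 8.5.1, and Section 13.10 does the same for accrual. None of them adds a rule for death.

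**The concern.** Neither dose-level sentence mentions grade 5, death, or grade 4 and above. Because the scale in use makes death a category of its own, a death is not, on the face of the text, a grade 4 toxicity. The rule would then be strict about a life-threatening event that the patient survives and silent about one that kills.

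The case is not far-fetched for this product. Section 6.2 says that the vaccine has not been given to humans before, and it lists both a severe allergic reaction and a severe autoimmune reaction as rare risks that can be fatal. The two sentences decide whether more patients are exposed at a dose and whether the dose goes up, so they should give the right answer for the worst outcome without relying on interpretation.

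**Working it through.** There is no stated figure to reproduce. The check applies the written rules to defined cases.

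**Inputs.** The two rules are from Section 8.5.1. Arm size is n = 10 (Section 13.9) or up to 12 (Section 13.3). The grade scale is from Sections 3 and 11.1.3.

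**Notation.** Among attributable, non-exempt events in one arm, let *a*, *b* and *c* be the numbers of participants with at least one grade 3, grade 4 and grade 5 event. A participant may count in more than one, so no worst-grade convention is imposed.

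**Rules as written.** Escalation is allowed if *b* = 0 and *a*/n < 0.30. Accrual stops if *a* ≥ 3 or *b* ≥ 1. The count *c* appears in neither.

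**Amended rules.** Replace *b* by the number of participants with a grade 4 or a grade 5 event.

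| Case | Arm size | *a*/n | As written: escalate / stop | Amended: escalate / stop |
|---|---|---|---|---|
| A. One survivable grade 4 | 10 or 12 | 0% | no / yes | no / yes |
| B. One death, grade 5 only | 10 or 12 | 0% | **yes / no** | no / yes |
| C. One death, same patient also has grade 4 | 10 or 12 | 0% | no / yes | no / yes |
| D. One death, grade 5 only, plus two others with grade 3 | 10 | 2/10 = 20% | **yes / no** | no / yes |
| D | 12 | 2/12 = 16.7% | **yes / no** | no / yes |
| E. One death, grade 5 only, plus three others with grade 3 | 10 | 3/10 = 30% | no / yes | no / yes |
| E | 12 | 3/12 = 25% | yes / yes | no / yes |

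Both decisions go wrong exactly when *c* ≥ 1, *b* = 0 and *a* ≤ 2. With *a* ≥ 3 the grade 3 limb already stops accrual.

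**The early pause.** Section 3 says that "three patients will initially be enrolled to a dose arm, receive the first vaccine, and be evaluated for toxicity prior to the second vaccine" before the rest of the arm is enrolled. It gives no threshold for that evaluation. Applying Section 8.5.1 at n = 3 to case B again gives no stop.

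**Does the amendment disturb anything else?** Without grade 5 events, each participant is in one of four classes (neither grade, grade 3 only, grade 4 only, both). The number of possible count patterns is C(n+3, 3):

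- n = 10: 13 × 12 × 11 / 6 = 286
- n = 12: 15 × 14 × 13 / 6 = 455

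In all of these the amended count equals *b*, so the decision differs in 0 of 286 and 0 of 455.

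**The case against.** Six points can be made for leaving the text alone.

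1. **The trigger is what a participant experiences, not what is recorded.** A fatal allergic or autoimmune reaction would usually pass through a life-threatening phase, which is grade 4. This narrows the gap, and case C shows that the rule then works. But the protocol does not say that a fatal event also counts as grade 4, and the stop should not turn on that choice.
2. **Bare grades can be read as floors.** The patient-level text moves from grade 3 or above to plain grade 3 in consecutive sentences and evidently means the same thing. A floor at grade 4 could sit beside a separate grade 3 limit. This reading is plausible and probably intended, but it is not secured. The section writes the floor explicitly only for the individual patient, and the escalation sentence ties the decision to the rate of each named toxicity.
3. **Meeting the benchmark only permits escalation.** Section 13.10 requires toxicity review with NCI/DCP staff before each step. That is true, but the same section says the decision follows Section 8.5.1, and the review does nothing about accrual in the current arm by rule.
4. **Other safeguards would act.** These are the one-week gap after the first patient in each arm, meant to exclude toxicity, the three-patient evaluation, 24-hour reporting of serious events (Section 11.2.2) and the funding sponsor's right to stop (Section 8.5). The one-week gap does serve for the first patient in each arm during that week. The others are reporting or discretionary steps, or carry no threshold.
5. **The incorporated monitoring plan and its addendum (Section 12.4) may contain a rule for deaths.** They were not available, so this stands as a limit on the finding.
6. **It is only wording.** The edit is small, but the sentences are the operative safety rule, and read literally they give the wrong decision for the gravest event.

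**Conclusion.** The gap is real on the text. In an arm of 10 or 12, an attributable death with no grade 4 event counted, and with at most two participants having non-exempt grade 3 toxicity, meets the escalation benchmark and triggers no accrual stop. One survivable grade 4 event does the opposite on both counts.

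The conclusion rests on a literal reading of Section 8.5.1 and on the fatal course not also being counted as grade 4. It concerns what this document states, not what the trial team would do; a halt would very likely follow in practice. The event is rare and the documents give no rate for it, so no probability is attached. The wording should be corrected because the consequence is the most serious one that the rule can face and the intended meaning is hardly in doubt.

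**What to change.** In Section 8.5.1, write *grade 4 or higher* in place of *grade 4* in two places: the escalation benchmark and the accrual-stopping sentence. Sections 3, 13.1 and 13.10 then inherit the correction, since they point back to Section 8.5.1.

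The autoimmune sentence in the same section also stops at grade 4, and the second patient-level sentence uses a bare grade 3. Aligning them would be tidy but is not needed to close this gap.

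The cost is two short edits in one section, made through an amendment approved by DCP and the IRB (Section 14.3). No decision based on grade 3 or grade 4 events alone changes, and no endpoint, sample size or analysis is affected.

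### The optional steroid taper in section 8.5.1 has overlapping day ranges, so days 4, 5 and 6 each carry two different prednisone doses

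*Combined protocol and SAP*

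**What the plan says.** Section 8.5.1 (Criteria for Premature Study Termination) says that the investigators "would consider steroid administration for grade 3 or 4 adverse immune related events" and introduces the taper with "The following dose schedule may be used". Six lines follow:

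- The opening line, the only intravenous one, is "Day 1-2: Intravenous Solu-Medrol at 1 mg/kg".
- The oral part of the taper then begins with "Day 3-4: Prednisone at 30 mg BID PO q day".
- The third line, which starts where the second ends, is "Day 4-5: Prednisone at 15 mg BID PO q day".
- The fourth line, which starts where the third ends, is "Day 5-6: Prednisone at 10 mg BID PO q day".
- The fifth line, which starts where the fourth ends, is "Day 6-7: Prednisone at 10 mg PO q day".
- The closing line, which stands clear of the fifth, is "Day 8-9: Prednisone at 5 mg PO q day".

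The first and last lines share no day with their neighbours. The four lines between them each start on the day the previous one ends, except that the first of the four starts cleanly on day 3. No other section gives a steroid schedule or a rule for a day that falls in two lines.

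**The concern.** A taper should give one dose for each day. Here three consecutive days fall in two lines each, and the two lines give different daily amounts. The lines are complete and in order, so this does not look like a fault of text extraction.

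What is at stake is the consistency of treatment for a severe event. Section 5 names two administering institutions. Clinicians at each could follow the printed schedule in good faith and give different amounts for the same event. Section 6.2 states that this is the first use of the vaccine in humans and lists a severe autoimmune reaction among the rare risks. A schedule offered for such events should therefore be readable in only one way.

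**Working it through.** **Inputs.** All come from the six lines in section 8.5.1. The plan gives no daily or total amount of its own, so there is no figure to reproduce. Assumption: BID means two doses a day, so the daily amount is the unit dose times 2. For a once-daily line it is the unit dose. The intravenous line for days 1 and 2 is weight-based and is left out of the prednisone total.

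**Step 1: daily amount for each line.**

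- Days 3-4: 30 × 2 = 60 mg
- Days 4-5: 15 × 2 = 30 mg
- Days 5-6: 10 × 2 = 20 mg
- Days 6-7: 10 × 1 = 10 mg
- Days 8-9: 5 × 1 = 5 mg

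**Step 2: lines that cover each day, ranges read as inclusive.**

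| Day | Lines covering it | Prednisone, mg/day |
|---|---|---|
| 1, 2 | one (intravenous) | none |
| 3 | one | 60 |
| 4 | two | 60 or 30 |
| 5 | two | 30 or 20 |
| 6 | two | 20 or 10 |
| 7 | one | 10 |
| 8, 9 | one | 5 each day |

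**Step 3: total for days 3 to 9.**

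- Higher line on every shared day: 60 + 60 + 30 + 20 + 10 + 5 + 5 = 190 mg
- Lower line on every shared day: 60 + 30 + 20 + 10 + 10 + 5 + 5 = 140 mg
- Difference: 30 (day 4) + 10 (day 5) + 10 (day 6) = 50 mg

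With two options on each of three days there are 2 × 2 × 2 = 8 combinations, so 140 to 190 mg is a range rather than a pair of outcomes.

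**Step 4: can another reading of the ranges remove the overlap?**

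- Counting only the start day of each range removes the overlap but leaves days 2, 7 and 9 with no dose.
- Counting only the end day removes it but leaves days 1, 3 and 8 with no dose.
- A tie-break rule would give one dose a day. If the earlier line governs a shared day the total is 190 mg. If the later line governs it is 140 mg. The section states neither rule.

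**Step 5: dependence on the BID assumption.** Three lines print a twice-daily and a once-daily abbreviation together. If the once-daily term governed them, day 4 would be 30 or 15 mg and day 5 would be 15 or 10 mg, while day 6 would be 10 mg on both lines. The conflict on days 4 and 5 therefore does not depend on the assumption; the one on day 6 does.

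**The case against.** The strongest reply is that the schedule is discretionary twice over: steroids are to be considered, and the schedule is one that may be used. A clinician who departs from it breaks no protocol rule. Six of the nine days are unambiguous and the direction of the taper is clear. This stands, and it limits the weight of the point. A reader might infer that the schedule cannot be followed at all. The documents support only that it is ambiguous on three transition days. Being optional does not remove that ambiguity for a clinician who does choose it.

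A second reply is that BID beside q day can simply mean twice a day, every day. That is a fair reading, and it is the one used in the figures above. The pairing is at most a secondary untidiness, and the point does not rest on it.

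A third reply is that few patients, if any, will need the schedule. Section 2.2 reports no clinical autoimmune disease in the 66-patient study of the HER2 plasmid, and section 13.8 expects no significant toxicity at any dose level. This also stands. It lowers the urgency but does not change what the lines say.

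Three stronger inferences are tempting but are not supported:

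- **Escalation or stopping.** Under section 8.5.1 dose-limiting status depends on grade and attribution. The table of allowable durations does not list autoimmune events. The line chosen on days 4 to 6 therefore does not decide that status or the escalation decision.
- **Recorded duration of toxicity.** Section 13.4 summarises duration descriptively, and nothing in the documents shows that the choice of line would shift it measurably.
- **The main safety concern of the trial.** The documents monitor for autoimmunity, but they also single out hyperglycemia, with an exclusion in section 4.2 and a vaccine-hold rule in section 8.5.1.1. They do not rank the two.

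Adding the two lines together on shared days would give 60 + 90 + 50 + 30 + 10 + 5 + 5 = 250 mg. That is implausible for a taper and is not part of the range given here.

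**Conclusion.** The point holds as an internal contradiction in an optional treatment schedule. Days 4, 5 and 6 each carry two prednisone amounts: 60 or 30, 30 or 20, and 20 or 10 mg. The total for days 3 to 9 is undetermined between 140 and 190 mg. These figures assume that BID means twice daily and that the day ranges are inclusive. The consequence is confined to patient management: a clinician using the schedule cannot tell which line applies on those days, and the two sites could differ. No sample size, power, error rate, dose-limiting toxicity classification or analysis is affected. The lines should be corrected because they concern the treatment of severe events and are wrong as printed, but they do not put the trial's design in question.

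**What to change.** The clinical leads should reconcile the schedule lines in section 8.5.1 so that each day appears once, with one dose and one frequency. The same edit should leave a single frequency term on the three lines that now print two. No dose, day range or tie-break rule is proposed here; that is a clinical decision.

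The correction is small but touches several lines, because the overlap runs across four of them. Under section 14.3 it goes to the DCP Protocol Information Office as an amendment and needs IRB approval before use, so it could sensibly be combined with the next planned amendment. No analysis text, sample size or data collection needs to change.

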
#### 8.5.1.1 Blood Glucose Monitoring

If random blood glucose is  $\geq 140$  mg/dl

1. Vaccine will be held and fasting glucose should be performed within a week:
  - a. If fasting glucose is  $\geq 100$  mg/dl patient should have a repeat fasting glucose done within 1 week
  - b. If fasting glucose is  $< 100$  mg/dl patient can receive vaccine
  - c. If this repeat fasting glucose remains  $\geq 100$  mg/dl patient will not receive additional vaccinations.

Patients who do not receive any more vaccines should continue to be followed for adverse events and immunogenicity.

For hyperglycemia with symptomology, please contact the IND Sponsor and DCP Medical Monitor.

## 9. CORRELATIVE/SPECIAL STUDIES

### 9.1 Rationale for Methodology Selection

#### 9.1.1. Immunogenicity of the 3 doses will be evaluated by an assessment of the generation of IGFBP-2,

HER2, and IGF-1R specific T cells (both Th1 and Th2).

Cellular immune response will be defined by the magnitude of the Th1 (IFN-gamma (g)) vs. Th2 (IL-10) antigen specific immune response using ELISPOT. Successful immunization will be defined by generating a protein specific IFN-g precursor frequency greater than 1:20,000 PBMC for each antigen. In patients with pre-existent immunity, responses must augment over 2 times baseline for immunization to be considered successful.

Exploratory analysis will assess whether patients maintain a Th1 dominant immune response to all three antigens over time.

Antibody immunity will be assessed as an additional measure of a Th2 response.

A humoral immune response will be measured by ELISA and serum antibody avidity for IGFBP-2, HER2, and IGF-1R (using ELISA) to determine an avidity index (AI) before and after vaccination. Low avidity antibodies will have an AI <30%, moderate avidity antibodies 30-50% and high-avidity antibodies 51-100%. Patients will be considered to have developed an antibody response if antigen specific IgG antibodies are both detectable and have moderate to high avidity.

- 9.1.2. To detect persistent T cell memory, flow cytometry panels will be used to evaluate antigen specific central and effector memory phenotypes prior to vaccination and at 1 and 6 months after immunizations.
- 9.1.3. To detect modulation of Tregs and MDSC with vaccination, levels over the course of immunization will be assessed by flow cytometry of PBMC.

